1.3.3 Criteria for the selection of subjects

Subjects: This study will prospectively enroll English and Spanish speaking women 15-45 years of age seeking initiation of LNG-IUS for contraceptive purposes at the OHSU OB/GYNS clinics. They must have access to a reliable cell phone and must be willing to receive and respond to a daily text or email message to assess bleeding.

Exclusion criteria: Postpartum within six months, pregnant, breast-feeding, LNG-IUS prescribed to treat abnormal uterine bleeding, switching from DMPA, IUS removal and replacement, undiagnosed abnormal uterine bleeding pre-dating placement of IUS, bleeding dyscrasias, anticoagulation use, active cervicitis, allergy to tamoxifen, history of venous thromboembolism, current or past breast or uterine malignancy, use of medication contraindicated with tamoxifen (coumadin, letrozole, bromocriptine, rifampicin, aminoglutethimide, phenobarbital).

Additional exclusions prior to randomization: noncompliance with electronic bleeding diary; clinical evidence of IUD complication (e.g. heavy bleeding suspicious for expulsion (complete or partial); unusual pelvic pain; fever and clinical exam suggesting endometritis.

No vulnerable populations will be specifically recruited or included in this study. Subjects between the ages of 15-18 years of age may be enrolled in this study, but will not be considered a vulnerable population or children since research procedures involve providing birth control information and services.

1.3.4 Subject recruitment and allocation

We plan to recruit patients seeking LNG-IUS insertion through targeted recruitment at the OHSU OB/GYN clinics. The decision to initiate IUS use will be made by the patient prior to enrollment in the study. Women who are scheduled for LNG-IUS insertion in the OHSU Center for Women's Health will be screened by chart review and contacted by phone within three days before their visit. On this phone call, study staff will describe the study using standardized text and assess interest in participation.

We will also advertise on the OHSU website or with Craig's List, as other OHSU Women's Health Research Unit (WHRU) projects are advertised, targeting ads to women who are planning to initiate the LNG-IUS. Women who call the WHRU will be screened for inclusion/exclusion criteria and directed to an appropriate OHSU clinic for LNG-IUS insertion and study enrollment, if desired. These recruitment documents will refer to tamoxifen as "drug" or "medication," and not list the study drug by name (as was done in a previous study using the same drug - OHSU IRB#10228). We found in the last tamoxifen study that potential subjects were being misinformed by internet searches about the study drug prior to their visits, and that allowing subjects to learn about the drug directly from study staff avoided this misinformation and improved recruitment. A through discussion about the study drug, tamoxifen, will take place at the initial visit before enrolling women into the study to avoid any misinformation from the internet.

At the time of their clinic visit for IUS insertion, those women previously indicating interest and those we were not able to reach in advance will be approached by study staff with information about the study. The decision to obtain the LNG-IUS and the insertion process will be completed with the patient's medical provider independent of the study. Those women who are eligible based on inclusion/exclusion criteria and who are willing to participate will complete the informed consent and enrollment process as described in section 1.3.6.

Women who enroll in the study will track bleeding and spotting starting on the day after LNG-IUS insertion via response to daily automated text messages. Those who are compliant with text message diaries over the first 14 days (responding 12 or more days, approximately 90% response rate) will be invited by phone to return for study visit 1 (occurring between 14-21 days after IUS insertion). On this scheduling phone call, post-insertion exclusions will be reviewed. Eligible women scheduled for study visit 1 will be randomized by the OHSU research pharmacy on the day prior to their scheduled visit. We anticipate that ensuring compliance with preliminary data collection will help minimize loss to follow up or missing data after randomization. The baseline bleeding data may be used as a covariate in final analysis.

The OHSU research pharmacy will randomize subjects to tamoxifen or placebo through a computer-generated algorithm using a block size of six. Treatment allocation will be double-blinded and study investigators will not have access to the randomization scheme or treatment assignments. The research pharmacy will maintain allocation concealment until completion of the study. Study drug (oral tamoxifen 10mg) will be purchased and routed through the OHSU research pharmacy, and identical placebo will be compounded by the research pharmacy. At

study visit 1, each subject will receive a total of seven days of medication to take home (14 pills). They will be instructed to start this medication on day 21 after insertion of their LNG-IUS.

Women with inadequate responses to the text message diary (less than 12 of 14 days) during the 14-day observation period will be contacted by phone to confirm discontinuation from the study, and they will stop receiving automated text messages.

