Between IUS insertion and study visit 1 (occurring 14-21 days after insertion), baseline bleeding with the LNG-IUS will be prospectively collected using bleeding diaries. This data will be used later as a covariate in analysis. A co-investigator (ob/gyn physician) will call each subject after at least 12 days of bleeding data collection to review exclusion criteria and to schedule study visit 1 if appropriate, as described in section 1.3.4. Subjects reporting concerns with their IUS will be referred to their primary provider or scheduled for a triage visit in family planning clinic to be examined by a physician as clinically indicated.

At study visit 1, bleeding diaries will be reviewed, and VAS scales (0-100mm) will be completed to obtain baseline assessment of bleeding satisfaction with the LNG-IUS. Each subject will receive one bottle of their assigned medication. Participants will be instructed to begin use of the study medication on day 21 after the insertion of their LNG-IUS and continue to take a twice daily oral dose of 10 mg for seven days. Estimated time to complete this visit is 15 minutes. Participants will receive a single text message or email reminder on the day they are due to start study medication. There will not be any specimens collected at this visit and there will be no results to share with subjects.

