A second message will be sent one minute after the first to inquire whether subjects took the study medication that day. If the subject does not respond to the text or email messages, a second set of texts or emails (2) will be sent the following morning. The subject has only these two chances to report their bleeding information for that day, and otherwise must use the paper diary. Responses to the messaging system will be compiled in a secured web database by Mir3, which can be accessed by research staff for data retrieval and entry onto research computers. Paper diaries will also be provided for use in case of technical difficulty in receiving or responding to text or email messages. Subjects are encouraged to complete paper diaries in addition to the electronic diary.

Follow up visits

Thirty days after initiating study drug, participants will receive an email with a link to a final study online survey via REDCap (attached). This survey will include questions assessing side effects, adverse events, and bleeding and IUS satisfaction. The satisfaction questions will utilize an electronic 100-mm visual analog scale. This study survey should take approximately 5-10 minutes to complete. Subjects not returning the survey within 7 days will be contacted by phone, text or email (based on stated contact preferences) and reminded to reply.

Compensation

Subjects will be compensated \$10 at enrollment and \$30 at the first study visit, which totals \$40. Additionally, subjects will be provided with compensation for completing the electronic bleeding diaries after use of study drug. Subjects will receive an additional \$1 each day that they respond to the electronic messages (up to 30 days total) and \$20 for completing the final survey. This is a total of up to \$50 that they can earn from completing the diaries and completing the study. The total compensation per subject is a maximum of \$90. Compensation will be loaded onto a debit card, which participants will receive at the enrolment visit.

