1.3.9 Criteria for discontinuation

Patients have the right to withdraw from the trial at any time on their own request for any reason; the reason for withdrawal will be recorded in detail. Subjects wishing to discontinue their LNG-IUS while enrolled in the study will terminate their participation with the study as of IUS removal. These subjects will be asked to complete the final online study survey prior to IUS removal to review bleeding profiles and satisfaction questions. No further data will be obtained from the patient once withdrawal occurs. Any data obtained up to this point will be analyzed in accordance with intention to treat.

We will have close contact with participants through the daily electronic bleeding diary. Failure to respond to the bleeding diary for three consecutive days will prompt a phone call from the study coordinator to inquire about technological difficulties versus disinterest in the study. If we are unable to reach a subject by phone, email or letter over two weeks, their participation will be terminated. Likewise, subjects declining to return for the study visit or complete the final survey will be discontinued from the study. Any data obtained up to this point will be analyzed in accordance with intention to treat.

If a subject becomes pregnant while participating in the study, her participation will be discontinued. She will be asked to come in for a study visit with the investigator. Her study medication will be unblinded and she will receive counseling from the investigator on how to seek medical care.

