1.3.11 Data analysis

Data will be extracted and entered into STATA on a password-protected computer. Analysis will be performed with the blinded data. P value of 0.05 defines statistical significance. Randomization will be assessed and if there is imbalance found between treatment and placebo groups, regression analyses will be completed to accommodate these differences.

Primary objectives: The primary measurement for this study will be the mean number of bleeding or spotting (b/s) days experienced by participants in the treatment group compared to placebo group over 30 days after treatment initiation. We will record baseline data on b/s days in the 21-day run-in period to confirm that the randomization was successful in allotting women with equivalent baseline b/s days to each group. Each day, subjects will indicate via numeric coded text or email message response whether they had spotting, bleeding, or none. From these diaries, counts of total bleeding/spotting days will be obtained. Other secondary bleeding outcomes will be examined including number of bleeding/spotting episodes, the number of prolonged bleeding episodes (>8 days), and the longest bleeding-free interval. Comparisons between groups will be made using an independent sample two sided t-test. Data will be analyzed in an intention-to-treat fashion. If data are very skewed, non-parametric methods will be used to compare groups.

Secondary objectives:

1. Satisfaction and side effects

At the study visit and in the final survey, subjects will answer questions regarding their satisfaction with the IUS and their bleeding patterns, acceptability of bleeding, as well as side effects and adverse events. Satisfaction responses will be quantified using a visual analog scale between 0-100mm. Discontinuation from the study and discontinuation of the IUS during the study will be monitored as markers of dissatisfaction. Comparison of means between tamoxifen and placebo groups will be made using two sided t-tests, and side effects will be reported descriptively.

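### Randomising the day before visit 1, when drug is handed over only at the visit, lets a no-show become a randomised, untreated woman who by default has no primary outcome; randomising on attendance would avoid this at a small cost

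*Combined protocol and SAP*

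**What the plan says.** Women keep a diary from insertion. Those who answer on at least 12 of the first 14 days are telephoned, have the post-insertion exclusions reviewed, and are booked for visit 1 between days 14 and 21 (section 1.3.4). Then: "Eligible women scheduled for study visit 1 will be randomized by the OHSU research pharmacy on the day prior to their scheduled visit". The stated purpose of the run-in is that "ensuring compliance with preliminary data collection will help minimize loss to follow up or missing data after randomization".

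Drug is dispensed at the visit itself. Section 1.3.6 says of visit 1: "Each subject will receive one bottle of their assigned medication". Section 1.3.4 says the same, and no other dispensing route is described. Dosing starts on day 21.

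Section 1.3.9 provides that "subjects declining to return for the study visit or complete the final survey will be discontinued from the study", and also: "If we are unable to reach a subject by phone, email or letter over two weeks, their participation will be terminated". Data obtained up to that point are analysed by intention to treat. The primary outcome in section 1.3.11 is bleeding/spotting days "over 30 days after treatment initiation". Section 1.3.2 treats days 22-51 after insertion as the matching period.

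**The concern.** Attendance at visit 1 is the last step before a woman can receive treatment, yet allocation is made one step earlier. Non-attendance, which could have been attrition before randomisation, therefore becomes attrition after it. That works against the stated purpose of the run-in.

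A randomised non-attender can go one of two ways. If she declines the visit or cannot be reached, section 1.3.9 discontinues her before day 22; she contributes baseline diary data and no primary outcome. If she misses the visit but goes on answering the remote diary, no rule addresses her, and under intention to treat she counts untreated in her allocated arm. Payment does little to keep her in the diary: section 1.3.7 says "subjects will be provided with compensation for completing the electronic bleeding diaries after use of study drug", and no diary payment is stated for a woman who never had drug.

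At stake is some power in a trial whose planned size leaves almost none to spare after the full dropout allowance. The exclusions that apply before randomisation (section 1.3.3) are also reviewed only on the scheduling call, so a problem arising between the call and the visit comes to light after allocation.

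**Working it through.** **Inputs.** From section 1.3.2: difference 7 days (40% of 18 is 7.2, written as 7), SD 7, 42 women in two arms of 21, 20% dropout, 80% power, alpha 0.05. From section 1.3.11: two-sided independent t-test.

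**Assumptions not in the documents.** Number of no-shows k = 2, 4 or 6 of 42 (5%, 10%, 14%), split evenly between arms; later loss L = 10% as an illustration; 42 read as the number randomised.

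**1. The plan's own figure.** The t-test needs 16.71 evaluable women per arm. 16.71 / 0.8 = 20.9, so 21 per arm and 42 in total. This reproduces the plan. After 20% loss there are 21 × 0.8 = 16.8 per arm and power is 80.2%; with no loss it is 88.5%.

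**2. No-shows counted inside the 20%.** Still 16.8 per arm, so power stays at 80.2%.

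**3. Later loss that can still be absorbed.** The plan needs 42 × 0.8 = 33.6 evaluable women. The tolerable later loss is 1 − 33.6 / (42 − k): 20% for k = 0, then 16.0%, 11.6% and 6.7% for k = 2, 4 and 6.

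**4. No-shows lost, plus later loss.** Evaluable per arm: n = (42 − k)(1 − L) / 2.

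| k | n, L = 10% | Power | n, L = 20% | Power |
|---|---|---|---|---|
| 0 | 18.9 | 84.9% | 16.8 | 80.2% |
| 2 | 18.0 | 83.0% | 16.0 | 78.1% |
| 4 | 17.1 | 80.9% | 15.2 | 75.9% |
| 6 | 16.2 | 78.7% | 14.4 | 73.4% |

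The L = 20% columns place no-shows on top of a full 20% later loss.

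**5. No-shows kept in the analysis untreated.** Let q = k / 42, and assume that an untreated woman in the tamoxifen arm bleeds like a placebo woman. The expected difference is 7(1 − q). The tamoxifen arm is then a mixture with variance 49 + q(1 − q) × 49, and the SD used is the square root of the mean of the two arms' variances. With L = 10%, n = 18.9 per arm.

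| k | Difference (days) | SD | Power |
|---|---|---|---|
| 2 | 6.67 | 7.08 | 80.4% |
| 4 | 6.33 | 7.15 | 75.5% |
| 6 | 6.00 | 7.21 | 70.2% |

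**The case against.** The strongest reply is that hardly anyone will be affected. Women who reach allocation have answered at least 12 of 14 messages, spoken to a physician co-investigator, accepted an appointment, and will be paid $30 for attending. Section 1.6 cites loss below 20% in similar studies and expects less here. Nothing separates no-shows from other dropout, so counting them inside the 20% is the natural reading. A woman who misses an early appointment might be rebooked before day 21, although the documents do not say so. All of this stands, and it is why the loss should be called small. Six of 42 is hard to support.

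A reader might infer more than the documents allow, in four ways:

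- **Bias between arms.** Allocation is blinded and no drug has been given, so attendance should not depend on arm.
- **Dilution as the usual result.** Section 1.3.9 makes loss of the outcome the default. Dilution requires a woman to stay away without declining, never rebook, and still complete the diary.
- **An undefined outcome window.** Section 1.3.11 does count from treatment initiation, but the project summary fixes treatment at 21 days after insertion within 51 diary days, and section 1.3.2 uses days 22-51. A window for an untreated woman can be inferred.
- **A wrong sample size.** It reproduces exactly.

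A further objection is that the change is partial: up to seven days remain between visit 1 and the first dose, and a woman can fail to start in that time too. That is correct. The change removes one cause of untreated randomised women, not all of them.

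**Conclusion.** The point holds as an inexpensive improvement to the design, not as an error that threatens the result. The sequence is explicit, and nothing elsewhere in the protocol prevents a non-attender from being randomised, untreated and, by default, without a primary outcome.

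The size rests wholly on assumed no-show rates. Within the dropout allowance there is no loss against the planned 80.2%. With 10% later loss and 2 to 6 no-shows lost, power falls by about 2 to 6 percentage points and drops below 80% only at 6. The larger losses in step 5 belong to the less likely case in which no-shows stay in follow-up. If the 42 in section 1.3.2 means enrolled rather than randomised, a non-attender uses up a place under either sequence; the change then saves no place and only keeps untreated women out of the randomised set.

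**What to change.** In section 1.3.4, move randomisation to visit 1, after the woman has attended and it is confirmed that no post-insertion exclusion has arisen since the scheduling call. One way is to assign the next blinded, sequentially numbered bottle that the pharmacy has prepared from its block-of-six list.

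The cost is protocol wording and a small change of pharmacy workflow, which the pharmacy must confirm because the documents do not describe its capacity. If 42 is the number randomised, each no-show is replaced by one further run-in enrolment. Visits, blinding, the block list and the number randomised stay as they are.

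If the pharmacy cannot work this way, section 1.3.9 should at least state whether a randomised woman who was never given drug continues the diary, and over which days and in which analysis she counts. That clarifies the handling but does not prevent the loss.

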1.3.5 Description of the drug to be studied

Tamoxifen is a nonsteroidal agent with antiestrogenic properties. Following an oral dose of 20mg, peak plasma concentration occurs about five hours after dosing. The elimination half-life is 5-7 days. Administration of 10mg tamoxifen given twice daily for three months results in average steady-state plasma concentration of 120ng/ml, which occurs after four weeks of continuous dosing (31). After oral administration, tamoxifen undergoes metabolism to its primary N-desmethyl tamoxifen metabolite, which has similar biologic activity to tamoxifen. It is a substrate of cytochrome P-450 3A, 2C9 and 2D6, and is an inhibitor of P-glycoprotein. Excretion is primarily fecal (31).

Tamoxifen is approved by the US Food and Drug Administration at doses of 20-40mg daily (divided dosing twice daily) and is primarily utilized for its antiestrogen properties as an adjuvant therapy to prevent recurrence of estrogen receptor (ER) positive breast carcinoma in post-menopausal women following mastectomy, axillary dissection and breast irradiation. It is also approved to reduce the incidence of breast cancer in high risk women (those with a 5 year predicted risk over 1.67% according to the Gail Model). Usual dose and duration of therapy is 20-40mg daily taken for up to five years.

When tamoxifen has been used previously at a dose of 10mg twice daily for 10 days in premenopausal women as a treatment for progestin-induced bleeding, side effects were rare and did not differ between treatment and placebo. The most common reported effect was headache, reported in up to 20% of users (2). There are reported serious adverse effects from long term tamoxifen use, but the short course of therapy in this study is unlikely to result in any of these adverse events. Risks with longer term use of tamoxifen may include endometrial changes such as hyperplasia, polyps, or malignancy, risk of venous thromboembolism, stroke or ovarian cysts. Of note, venous thrombosis events were not reported until at least two consecutive months of use. Likewise, an increased risk of endometrial cancer has only been demonstrated in postmenopausal women with use between 1 and 61 months. Increased incidence of endometrial hyperplasia and polyps have been reported only in postmenopausal women. A few reports of fibroids, endometriosis, and ovarian cysts have been observed in a small number of premenopausal women with advanced breast cancer receiving tamoxifen (31).

Use of tamoxifen for this study is exempt from the requirements to submit an Investigational New Drug application to the FDA. This study is not intended to be used for support of new FDA indication for use or labeling for tamoxifen. This study is also not intended to support a significant change in advertising for tamoxifen. Lastly, this study does not use a route of administration or dosage level that is known to significantly increase the risks associated with use of tamoxifen. As the dosage used in this study will be 10mg twice daily for seven days, it is anticipated that associated side effects will be rare and mild as previously reported when tamoxifen was used for a similar purpose for a 10 day course (2). In trials that have shown a non-statistically significant increased risk of pulmonary embolism and stroke in patients taking tamoxifen, >85% of these events have occurred in women 50 years of age or older who will not be included in this study (31). More severe side effects as noted above are typically not seen until higher dosages for longer periods of time than will be administered in this study.

